12.2 Record Retention

The investigator agrees to keep the records stipulated in Section 12.1 and those documents that include (but are not limited to) the study-specific documents, the identification log of all participating subjects, medical records, temporary media such as thermal sensitive paper, source worksheets, all original signed and dated informed consent forms, subject authorization forms regarding the use of personal health information (if separate from the informed consent forms), copies of all paper CRFs and query responses, including the audit trail, and detailed records of drug disposition to enable evaluations or audits from regulatory authorities, the sponsor or its designees. Any source documentation printed on degradable thermal sensitive paper should be photocopied by the site and filed with the original in the subject's chart to ensure long term legibility. Furthermore, International Conference on Harmonisation (ICH) E6 Section 4.9.5

requires the investigator to retain essential documents specified in ICH E6 (Section 8) until at least 2 years after the last approval of a marketing application for a specified drug indication being investigated or, if an application is not approved, until at least 2 years after the investigation is discontinued and regulatory authorities are notified. In addition, ICH E6 Section 4.9.5 states that the study records should be retained until an amount of time specified by applicable regulatory requirements or for a time specified in the Clinical Study Site Agreement between the investigator and sponsor.

Refer to the Clinical Study Site Agreement for the sponsor's requirements on record retention. The investigator should contact and receive written approval from the sponsor before disposing of any such documents.

13.0 STATISTICAL METHODS

13.1 Statistical and Analytical Plans

A statistical analysis plan (SAP) will be prepared and finalized prior to unblinding of subject's treatment assignment. This document will provide further details regarding the definition of analysis variables and analysis methodology to address all study objectives. A data review, blinded for the main period, will be conducted prior to database lock. Data handling issues and exploratory analyses may be changed due to unforeseen reasons after the blinded data review. All later deviations and/or alterations will be documented and summarised in the Clinical Trial Report.

Statistical analysis will be performed by the Sponsor's representative. The final statistical analysis must be approved by the Sponsor.

13.1.1 Analysis Sets

The following refers only to the evaluation of clinical data.

Analyses will be based on the following sets: total set, safety set, full analysis set, valid cases set. The definitions of the analysis sets are in consistency with those given in the ICH E9 Guideline (1998).

13.1.1.1 Total Set

The total set consists of all Subjects enrolled, including Subjects withdrawn prior to randomization (defined as non-eligible Subjects) and those randomized Subjects, who never took any dose of the trial treatment after randomization (defined as randomized but not treated Subjects).

13.1.1.2 Safety Set

The safety set (SAF) is based on all randomized Subjects who took at least one dose of the trial treatment after randomization. Safety analyses will be based on the SAF. For the safety analyses Subjects will be assigned to the treatment they actually received ('as treated' analysis). In addition, analyses for baseline AEs will be performed on the total set.

13.1.1.3 Full Analysis Set

The full analysis set (FAS) includes all randomized Subjects who took at least one dose of the trial treatment after randomization. In case Subjects were randomized and treated more than once, only the first randomization (and treatment) of the Subject will be included in the FAS.

The Intention-to-treat (ITT) analysis will be based on the FAS. Subjects will be assigned to the treatment group based on the treatment to which they were randomized ('as randomized' analysis).

The ITT analysis will be the primary analysis for this trial and will be performed for all primary and secondary endpoints.

13.1.1.4 Valid Cases Set

The valid cases set (VCS) consists of all Subjects of the FAS without any major protocol violations. Subjects terminating prematurely will be included in the VCS provided that there is no major protocol violation.

Subjects with major protocol violations considering the inclusion criteria, randomization criteria, and criteria affecting the read-out parameters of the trial will be identified during review of the blinded data. Violation of the criteria within ethical considerations in terms of general health are considered minor deviations in terms of impact on interpretability of the data, but it will be assessed during review of the blinded data if there is an impact for single cases. Deviations occurring during the following procedures will not be considered major protocol violations for the primary objective of the trial: Telephone contacts after early withdrawal and follow-up visit after regular trial end.

The Per-Protocol (PP) analysis is based on the VCS. In analogy to the ITT analysis it will be performed on an 'as randomized' basis.

The PP analysis will be used to assess the robustness of the results and will be performed for the primary and key secondary endpoints (see Section 13.1.3.2) only.

13.1.2 Analysis of Demographics and Other Baseline Characteristics

Demographic and baseline characteristics will be summarized by each treatment group and overall. Summary statistics (N, mean, SD, median, minimum, and maximum) will be generated for continuous variables (eg, age and weight) and the number and percentage of subjects within each category will be presented for categorical variables (eg, sex, and race). Individual subject demographic and baseline characteristics data will be listed.

13.1.3 Efficacy Analysis

For the primary analysis all data until a Subject discontinued (prematurely or as scheduled) will be included. All data that was captured after a Subject discontinued the trial or at the Follow-up visit (V7) will be included in descriptive analyses. These additional analyses will be considered as ITT analyses.

The analysis of primary and secondary endpoints will be based on the FAS, the subset of the FAS without exacerbation during double-blind treatment, and the VCS (see below for details).

13.1.3.1 Primary analysis of primary and key secondary endpoints

The primary analysis will be performed in the FAS.

The **primary variable** relates to pulmonary inflammation expressed as inflammatory CD8+ cell counts per mm² in sub-mucosal bronchial biopsy tissue specimen measured before and after the double-blind treatment period (i.e. at V2 and at V6). CD68+ cell counts per mm² in sub-mucosal bronchial biopsy tissue specimen at V2 and at V6 is the **key secondary variable**.

Roflumilast/placebo comparisons with respect to CD8+ and CD68+ will be done via a multiple test procedure such that the family-wise error rate of 5% is controlled in the strong sense. The two null hypotheses are: equal CD8+ counts/mm² and equal CD68+ counts/mm² on Roflumilast and placebo. These null hypotheses will be ordered, so that the CD8+ comparison comes first and the CD68+ comparison comes second. If the comparison with respect to CD8+ is significant at the nominal level $\alpha = 5\%$, the corresponding null hypothesis will be rejected and the CD68+ comparison will be performed in a confirmatory way (otherwise confirmatory testing stops). This will again be done at nominal level $\alpha = 5\%$. If significant (after a significant result in the first comparison), the corresponding null hypothesis will be rejected. If the first comparison is not significant at the nominal 5% level, then no null hypothesis must be rejected.

The component tests of the multiple test on CD8+ and CD68+ will be based on Poisson regression models with CD8+ (CD68+) at visit V6 as dependent variable and treatment and baseline value of the respective dependent variable as covariates. A dispersion parameter and an offset (= bronchoscopy sampling area) will be taken into account. A formal description of the model and test for an inflammatory cell is this:

Let Y_{ij} be independent random variables which represent numbers of inflammatory cells in tissue area t_{ij} for treatment i ($i=1$: Roflumilast, $i=0$: placebo) and Subject j . The Y_{ij} are assumed to follow a Poisson regression model with expectation $\gamma_i = E(Y_{ij} / t_{ij})$ (not depending on Subject) and a dispersion parameter. The log-link function is assumed for the model. Log-transformation of the expectation gives the following linear function

$$\log E(Y_{ij}) = \alpha + \beta_0 \cdot X_0 + \beta_1 \cdot X_1 + \log(t_{ij}),$$

where α is an intercept, X_0 is the baseline value (=cell count per mm² at baseline V2), X_1 the treatment indicator (1=Roflumilast, 0=placebo) and β_0 and β_1 are regression coefficients.

The null hypothesis is

$$H_0 : \beta_1 = 0.$$

This means that the number of cells per tissue area on Roflumilast and placebo are the same.

H_0 will be tested using the likelihood ratio statistic.

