6.0 STUDY DESIGN AND DESCRIPTION

6.1 Study Design

The total duration of this randomized, multicentre, phase III trial is 24 weeks maximum. It includes six weeks of single-blind placebo administration during the run-in period and 16 weeks of double-blind treatment, followed by a single safety visit (within two weeks) for subjects undergoing the second (final) bronchial biopsy.

This trial will be performed in Chronic Obstructive Pulmonary Disease (COPD) patients (GOLD stage II-III, **in Germany stage II only**) and will include two parallel treatment arms (placebo and Roflumilast 500 µg once daily). A 1:1 randomization scheme will be used, i.e. Subjects will be allocated to Roflumilast 500 µg or placebo in equal proportions. Randomization will be stratified by concomitant LABA use.

[figure not shown]
The trial consists of the following periods:

- **Single-blind placebo run-in period** (6 weeks) with visits scheduled at weeks: -6 (V0), -2 (V1) and 0 (V2, randomization visit).
- **Double-blind treatment period** (16 weeks) with visits scheduled at 6, 14, and 16 weeks of treatment (V4-V6). An additional visit V3 will have to be performed within two weeks after bronchoscopy/bronchial biopsy purely as a safety visit. The exact timing of this safety visit will be determined by the Investigator.
- **Safety follow-up.** All adverse events (AEs) will be followed up to 30 days after the double-blind treatment period has been completed. An additional safety visit V7 will be scheduled within 2 weeks after the second bronchoscopy. The exact timing of the safety visit will be determined by the Investigator.

A schematic of the study design is included as [Figure 6.a](#). A schedule of assessments is listed in [Appendix A](#).

Figure 6.a Schematic of Study Design

Single-blind run-in: 6 weeks	Double-blind treatment including Safety follow-up V3 for Subjects undergoing bronchoscopy 16 weeks	Safety follow-up including V7 for Subjects undergoing the second bronchoscopy 2 weeks
---------------------------------	---	--

Therapy consisting of any bronchodilator (SABA, SAMA, LABA, LAMA) or their combination in stable doses. Rescue medication: SABA or SAMA

Abbreviations: V2 – randomization visit and first bronchoscopy, V6 – visit at the end of double blind treatment period and second bronchoscopy, LABA – Long-Acting β_2 -Agonist, LAMA – Long-Acting Muscarinic Antagonist, SABA – Short-Acting β_2 -Agonist, SAMA – Short-Acting Muscarinic Antagonist, o.d. – once daily

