8.2 Investigational drug Assignment and Dispensing Procedures

The investigator or investigator's designee will access the IVRS/IWRS at Screening to obtain the subject study number and will utilize the IVRS/IWRS to randomize the subject into the study. During this contact, the investigator or designee will provide the necessary subject-identifying information, including the subject number assigned at screening. The medication identification (ID) number of the investigational drug to be dispensed will then be provided by the IVRS/IWRS. If sponsor-supplied drug (Roflumilast, 500 ug tablet, once daily and Placebo tablet, once daily) is lost or damaged, the site can request a replacement from IVRS/IWRS. (Refer to IVRS/IWRS manual provided separately.) If the label includes a tear-off portion, this will be affixed to the CRF. If there is no tear-off portion of the label, the CRF will be completed by hand writing the required information in the space provided on the form. At subsequent drug-dispensing visits, the investigator or designee will again contact the IVRS/IWRS to request additional investigational drug for a subject. The medication ID number of the investigational drug to be dispensed will be provided by the IVRS/IWRS.

In this trial, a 1:1 randomization is employed for both treatments, thus 150 Subjects will be treated with either Roflumilast 500 µg or placebo. Randomization will be stratified by concomitant LABA use, since the DAXAS[®] pivotal trial pool suggests LABA may be a confounding variable.

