13.1.3.2 Supportive analysis of primary and key secondary endpoints

The following analyses will be performed in the FAS, FAS without exacerbation during double-blind treatment and VCS.

- Descriptive: absolute and change variables (change from V2 to V6)
- ANCOVA on change variables (from V2 to V6) with covariates as in the primary analysis plus stratification factor as covariate. Point estimates of adjusted treatment differences will be presented with confidence intervals.

- Poisson regression with covariates as in the primary analysis without confirmatory testing (i.e. p-values associated with treatment effect are interpreted along exploratory lines). Point estimates of adjusted treatment ratios will be presented with confidence intervals.
- Descriptive: absolute and change variables (change from V2 to V6) in subgroups formed by COPD stage, smoking status, concomitant LABA use and former ICS use (4 subgroup analyses).
- Poisson regressions with covariates as in the primary analysis plus covariates indicating COPD stage, smoking status, concomitant LABA use and former ICS use (4 different models) without confirmatory testing. Point estimates of adjusted treatment ratios with confidence intervals will be presented

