13.1.5.3 Body weight and BMI

Weight change [kg] and BMI change [kg/m^2] will be analysed using an ANCOVA model including LOCF. The dependent variable will be the change from randomization (V2) to the last scheduled post-randomization visit up to visit V6. The following factors and covariates (all fixed) will be included in the model: treatment and baseline value.

In addition, pre-treatment with LABA (yes/no) will be included in the model as this is used as stratification factor in the randomization (CPMP/EWP/2863/99) [25].

Descriptive summary statistics (N, mean, SD, median, 68% range, minimum and maximum) will be provided for all scheduled visits (absolute values as well as changes from baseline) by treatment. A Subject data listing by treatment and visit will be provided showing body weight [kg] and BMI [kg/m^2] (absolute values as well as changes from baseline).

Further details regarding body weight and BMI will be given in the SAP.

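### The confirmatory CD8+ and CD68+ model omits LABA use, the stratification factor, without a stated reason; the likely cost is a little power, not validity.

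*Protocol*

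**What the plan says.** - **Design.** Section 6.1: "Randomization will be stratified by concomitant LABA use". Section 8.2 gives the reason: the "pivotal trial pool suggests LABA may be a confounding variable".
- **Confirmatory test.** Section 13.1.3.1 specifies a Poisson regression of the V6 count with "treatment and baseline value of the respective dependent variable as covariates", a dispersion parameter and the sampling area as offset. The linear predictor is written out: intercept, baseline count per mm² (X0), treatment indicator (X1) and log area. The hypothesis β1 = 0 "will be tested using the likelihood ratio statistic". The synopsis lists the same covariates. Because the formula is explicit, this is not a detail left to the SAP.
- **Supportive analyses of the same endpoints.** In section 13.1.3.2 the ANCOVA runs "with covariates as in the primary analysis plus stratification factor as covariate". One Poisson regression repeats the primary covariates. Four further exploratory Poisson models add COPD stage, smoking status, LABA use and former ICS use respectively.
- **Secondary endpoints.** In section 13.1.3.3 both the ANCOVA and the Poisson models carry baseline, treatment and the stratification factor.
- **Weight and BMI.** Section 13.1.5.3: "In addition, pre-treatment with LABA (yes/no) will be included in the model as this is used as stratification factor in the randomization", with a citation of the European guideline on baseline covariates.

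**The concern.** The protocol accepts in section 13.1.5.3 that a factor used to stratify randomization belongs in the model, and follows that in sections 13.1.3.2 (ANCOVA) and 13.1.3.3. It does not follow it in the test that carries the claim. As a result, submucosal neutrophils, CD4+ and CD45+ are compared with LABA in the Poisson model, while CD8+ from the same biopsies is compared without it.

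Stratified allocation balances LABA between arms. If LABA is related to cell density and is left out of the model, its variance stays in the dispersion estimate. The standard error of the treatment effect is then larger than the design warrants. What is at stake is some power for CD8+, and through the fixed testing order for CD68+ as well.

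**Working it through.** **1. The plan's own sample size.** Inputs from section 13.3: rates 200 and 285 cells/mm², dispersion φ = 25, area t = 0.3 mm², two-sided α = 0.05, power 90%.

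n per arm = (1.960 + 1.282)² · φ · (1/200 + 1/285) / (t · [ln(285/200)]²)
= 10.507 · 25 · 0.008509 / (0.3 · 0.12544) = 59.4, rounded up to 60, so 120 in total.

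This is the table's figure, and the formula returns all 24 cells of the table. It has no LABA term, so the point changes no stated sample size. At the expected 105 evaluable subjects the same formula gives 86.2% power.

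**2. What must be assumed.** The documents give neither the effect of LABA on CD8+ or CD68+ counts nor the share of LABA users. Below, 50% LABA use is assumed and the LABA rate ratio is varied.

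**3. Standard error with baseline in both fits.** Simulation with 104 evaluable, between-subject CV 0.55, 0.3 mm², 2,500 trials per scenario, LABA shifting density at both visits. Power is taken as Φ(0.354/SE − 1.960), with 0.354 = ln(285/200).

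| LABA shift | SE, LABA omitted | SE, LABA included | Power, omitted | Power, included |
|---|---|---|---|---|
| 20% | 0.1017 | 0.1008 | 93.6% | 94.0% |
| 40% | 0.1032 | 0.1007 | 92.9% | 94.0% |

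Omission makes the SE larger by 0.1017/0.1008 − 1 = 0.9% and 0.1032/0.1007 − 1 = 2.5%. The loss is 0.4 to 1.1 points.

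**4. Power with baseline in both fits.**

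- 104 evaluable, dispersion about 25, 0.3 mm², V2–V6 log-scale correlation 0.3, 3,000 runs:

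| LABA rate ratio | Power, omitted | Power, included | Loss (points) |
|---|---|---|---|
| 1.0 | 92.5% | 92.5% | 0 |
| 1.25 | 91.7% | 92.1% | 0.4 |
| 1.5 | 91.4% | 92.7% | 1.3 |
| 2.0 | 87.2% | 91.8% | 4.6 |

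- 105 evaluable, 0.3 mm², CV 0.53, correlation 0.3 or 0.6, 2,000 runs: loss of 0.2 to 0.6 points at ratio 1.25 and 0.6 to 2.1 points at 1.5, with Monte Carlo error of about 0.3 to 0.6 points.

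In the first of these two simulations, adding LABA cut the treatment SE by 2 to 11% over ratios 1.25 to 2.0, so the SE effect depends on the assumptions more than step 3 alone shows.

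**5. Type I error.** Simulation with 105 evaluable, within-stratum dispersion 25, 4,000 runs, likelihood ratio test scaled by the Pearson dispersion. Baseline was left out of both fits, which overstates the role of LABA.

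| LABA rate ratio | Type I error, omitted | Type I error, included |
|---|---|---|
| 1.0 | 5.5% | 5.5% |
| 1.25 | 4.7% | 5.1% |
| 1.5 | 3.9% | 5.1% |
| 2.0 | 2.5% | 5.8% |

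Monte Carlo error is about 0.4 points. Omission lowers the rejection rate under the null and does not raise it. Adjustment does not guarantee exactly 5%: with baseline in the model, lognormal heterogeneity and a prognostic LABA effect, the adjusted test's size ran at 5.2 to 6.9%.

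**The case against.** The strongest reply is that the adjusted model is already in the plan. Section 13.1.3.2 specifies the primary Poisson model plus LABA for both endpoints, in three analysis sets, with adjusted ratios and confidence intervals. The change only swaps which model is confirmatory. That is correct and limits the weight of the point. It does not remove it: the exploratory model cannot decide the CD8+ test or open the CD68+ test.

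Second, section 7.7 requires bronchodilators to have started at least six weeks before V0 and to stay stable throughout. The V2 biopsy is therefore taken on the same LABA regimen as V6, and the baseline count already carries part of any LABA effect. This stands, and is why the figures with baseline in the model are the relevant ones. If LABA nonetheless acted only at V6 with ratio 1.5, the simulation with 3,000 runs gives 90.4% against 93.2%, a loss of 2.8 points; nothing in the documents points to that case.

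Third, no document shows that LABA predicts CD8+ or CD68+ counts. Section 8.2 says only that it may be a confounder. The pivotal endpoints in section 4.2 are FEV1 and exacerbations, with similar effects whatever the LABA use. This also stands.

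A reader might infer that the confirmatory model is the only one without LABA, or that its covariates differ from those of every supporting analysis. Section 13.1.3.2 contradicts both: one supportive Poisson model repeats the primary covariates, and the models adding COPD stage, smoking status or former ICS use also omit LABA.

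**Conclusion.** The inconsistency is real and unexplained, and its practical cost is small. With baseline in the model, 50% LABA use and an assumed LABA rate ratio of 1.25 to 1.5 at both visits, leaving the stratum out costs roughly 0 to 2 power points. It costs nothing if LABA is unrelated to the counts.

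Larger losses appear only under stronger assumptions. The 4.6 points at ratio 2.0 need a LABA effect well above the planned drug contrast of 285/200 = 1.43. A loss near 8 points (80.4% against 88.0%) arises only at that ratio with baseline left out of both fits, which is not the protocol's model.

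A reader might also conclude that the primary test is invalid. It is not: the omission tends to make it conservative. The point is one of consistency and a small, nearly free gain in efficiency.

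**What to change.** - In the synopsis and section 13.1.3.1, add β2·X2 to the linear predictor of both confirmatory tests, where X2 is the stratification factor (concomitant LABA use yes/no, as randomized). Keep the model without LABA as a supportive analysis.
- Adjust section 13.1.3.2 to match. Its supportive analyses are defined by reference to the primary covariates, so they would otherwise change unintentionally; the exploratory Poisson model with LABA becomes the primary model.
- Use one definition of the factor throughout. Section 13.1.5.3 refers to LABA pre-treatment, while sections 6.1, 8.2 and 13.1.3.2 refer to concomitant use.
- If the sponsor prefers the present model, state the reason in section 13.1.3.1.

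Make the change before unblinding. It costs one degree of freedom and a few lines of text, and needs no new data.
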